2.2 Individual Post-Treatment Period Visit Activities

This section presents a list of activities performed during each visit, organized by visit. The dot pattern on the upper right indicates the place of the visit in the overall Post-Treatment Period Activity Schedule.

Activities are grouped by category (Interview, Exam, etc.). Further information about the activities is presented in Section 3.

p. 16 of 47

30-Day Follow-Up Visit/Calla:

AE assessment

Concomitant therapy

#,+ Urine pregnancy test^{b,c}

NOTES

- a. A Follow-Up Visit will occur approximately 30 days after the last dose of study drug to obtain additional safety information. For subjects that prematurely discontinued study participation and are willing to provide additional information, this visit may be a telephone call if a site visit is not possible. The Follow-Up visit is not applicable for subjects who discontinued study drug and continued study participation with completion of at least one study visit occurring at least 30 days after last dose of study drug.
- b. For all females of childbearing potential, collect urine for pregnancy test (refer to Section 3.19 for additional details).
- f. If urine pregnancy tests cannot be performed on-site or at home due to COVID-19, urine pregnancy tests may be performed by a local lab.

3 STUDY PROCEDURES

3.1 Screening Period

Within 35 days prior to the Baseline Visit, subjects will receive a full explanation of the study design and study procedures, provide a written informed consent, and undergo the screening procedures outlined in Section 2.1. With the exception of the QuantiFERON tuberculosis (TB)-Gold Plus and purified protein derivative (tuberculin) (PPD) tests (requirements outlined in Section 3.19), exclusionary laboratory values can be re-tested once during the Screening Period. If the retested lab value(s) remain(s) exclusionary, the subject will be considered a screen failure. Redrawing samples, if previous samples were unable to be analyzed, would not count as a retest since previous result was never obtained.

3.2 Rescreening

Subjects who initially screen-fail for the study are permitted to be re-screened once following reconsent. For additional re-screening, AbbVie Therapeutic Area Medical Director (TA MD)/Scientific Director approval is required. All screening procedures with the exceptions noted below will be repeated during rescreening. The subject must meet all eligibility criteria at the time of re-screening in order to qualify for the study. There is no minimum period of time a subject must wait to re-screen for the study.

If the subject had an initial screening evaluation including the following assessments, these tests will not be required to be repeated for re-screening, provided the conditions noted in Protocol Section 5.1 are met (Eligibility Criteria) and no more than 90 days have passed:

HBV, HCV, and HIV serology

- QuantiFERON TB Gold Plus or equivalent and/or a PPD test (or both if required per local guidelines)
- CXR
- ECG
- Beta-D-glucan (Japan only)

If a subject is being re-screened within 14 days (≤ 14 days have passed) from the collection date of the previous screening testing, it is not required to repeat Screening testing for chemistry, hematology, urinalysis, and serum pregnancy provided that the subject's health status has not changed to warrant a repeat test.

3.3 Study Subject Information and Informed Consent

The investigator or his/her representative will explain the nature of the study to the subject and answer all questions regarding this study. Prior to any study-related screening procedures being performed on the subject or any medications being discontinued by the subject in order to participate in this study, the informed consent statement will be reviewed, signed, and dated by the subject or their legally authorized representative, the person who administered the informed consent, and any other signatories according to local requirements. A copy of the signed informed consent will be given to the subject and the original will be placed in the subject's medical record. An entry must also be made in the subject's dated source documents to confirm that informed consent was obtained prior to any study-related procedures and that the subject received a signed copy.

Information regarding benefits for subjects and information regarding provisions for treating and/or compensating subjects who are harmed as a consequence of participation in the study can be found in the informed consent form.

Optional biomarker research samples will only be collected if the subject has voluntarily signed and dated a written consent form describing the exploratory research. The written consent may be part of the main consent form. If the subject does not consent to providing optional samples, the subject will still be allowed to participate in the study.

In cases of state of emergency or pandemic situations, it is possible that additional protocol modifications not outlined in this protocol may become necessary. If this situation arises, in addition to the study informed consent, additional verbal consent may be obtained prior to these adaptations or substantial changes in study conduct in accordance with local regulations.

3.4 Eligibility Criteria

Subjects will be evaluated to ensure they meet all eligibility criteria at both Screening and Baseline Visits.

3.5 Medical History

A complete non-study disease-related medical and surgical history, including demographics and history of alcohol and nicotine use, will be taken from each subject during the Screening Visit. Additionally, a list of each subject's specific disease-related medical and surgical history will be recorded at Screening. History of herpes zoster, herpes zoster vaccination, and hepatitis B vaccination status will be recorded as part of the medical history. The subject's medical history will be updated at the Study Day 1 visit. This updated medical history will serve as the baseline for clinical assessment.

3.6 Adverse Event Assessment

Please refer to Section 4.2.

3.7 Patient-Reported Outcomes

Data Collection

Subjects will complete self-administered patient-reported outcome (PRO) instruments. Subjects should be instructed to follow the instructions provided with the instrument(s) and to provide the best possible response to each item. Site personnel shall not provide interpretation or assistance to subjects other than encouragement to complete the tasks. Site personnel will encourage completion of the instrument at all specified time points and will ensure that a response is entered for all items.

PRO instruments that are administered at the site should be completed prior to drug administration and prior to any discussion of AEs or any review of laboratory findings. The subject should complete the questionnaire(s) before site personnel perform any clinical assessments and before any other interaction with site personnel has occurred to avoid biasing the subject's response.

From at least 7 consecutive days prior to the Baseline visit and up to the Week 16 visit, PGA Skin Pain will be collected from subjects using an electronic daily diary and analgesic use using a paper diary. After the Week 16 visit, PGA Skin Pain will be collected for 7 consecutive days leading up to the next scheduled visits as specified in Section 2.1. HSSA will be collected for 7 consecutive days prior to visits specified in Section 2.1. PGA Skin Pain will be collected from subjects electronically every evening using a handheld device provided to the subject at Screening. All data entered on the device will be immediately stored to the device itself, as well as automatically uploaded to a central server. Analgesic use for HS-related pain will be collected from subjects during the same timeframe by completing a paper diary. Data from the pain medication diary will be transcribed into the electronic data capture (EDC) system by study site staff.

Data from the DLQI and HSIA will be collected electronically at the visits specified in Section 2.1. Subjects will use a tablet device at the site to enter the required pieces of information. The electronic tablet device will be programmed to allow data entry for only the visits specified in the protocol and will not allow subjects to complete more than one of the same assessment at any one visit. All data entered on the tablet device will be immediately stored to the devise itself and automatically uploaded to a central server.

State of Emergency or Pandemic-Related Acceptable Protocol Modifications

During a state emergency or pandemic situation, subject visits may be conducted via phone or video conference. Patient-reported outcomes (DLQI and HSIA) are eligible for completion at these virtual visits, except Baseline and Week 12. If conducted by phone or video conference, sites will read the PRO questions and response options to the subject and record the subject's responses. The subject's ability to view the PRO to understand the questions and response options should be preserved. Sites may send the questionnaires (email or hard copy) to the subjects to allow them to read/understand the questions and responses when the subject is providing responses over the phone. The date and time of PRO data collection should be recorded along with who collected the information.

Patient's Global Assessment of Skin Pain

The PGA Skin Pain (Appendix 7.1) will be used to assess the worst skin pain due to HS. The scoring for PGA Skin Pain is based on an 11-point numerical rating scale (NRS), with ratings for the item ranging from 0 (i.e., no skin pain) to 10 (i.e., skin pain as bad as you can imagine). Patients are asked to respond to the items based on a recall period of "the last 24 hours." The weekly average score is calculated based on the 7 available daily scores from the days within each visit window that were closest to the nominal day.

Hidradenitis Suppurativa Symptom Assessment Questionnaire

The HSSA (24-hour recall) is a 9-item PRO questionnaire (Appendix 7.2) developed to assess the primary symptoms of HS in the 7 consecutive days prior to assessments. Each item of the HSSA is scored on an 11-point (0 to 10) NRS, where 0 represents no symptoms and 10 represents extreme symptom experience. In this way, item scores can be generated to characterize the subject's experience at a symptom level. Additionally, Items 1-9 can be scored together to create a Total Symptom Score to characterize an overall symptom experience by averaging the scores collected from the non-missing items collected at the same assessment. The weekly average score is calculated based on the 7 available daily scores from the days within each visit window that were closest to the nominal day.

Hidradenitis Suppurativa Impact Assessment Questionnaire

The HSIA is an 18-item PRO questionnaire (Section 7.3) developed to assess the impact of HS on the daily lives of subjects in the 7 days prior to the assessment. Items 1-16 of the HSIA are scored on a 0 to 10 NRS, where 0 represents no impact and 10 represents extreme impact. In this way, item scores can be generated to characterize the subject's experience at an individual impact level. Additionally, Items 1-16 characterize the overall impact of HS and can be scored together to create a weekly Overall HSIA score. The Overall HSIA score is generated by summing the completed individual impact, item-level scores collected on the same day, and dividing that sum by the total number of completed responses (i.e., the Overall HSIA score is an average). The Overall HSIA score will only be derived if eight or more (i.e., at least 50%) of responses are available (and adjusting the denominator to match the number of completed items). Items 17 and 18 utilize an open field where patients are asked to fill in a number, and are not included in the Overall HSIA score. Instead, a separate mean score for the hours worked (Item 17) or hours missed at school or work (Item 18) will be calculated. If the response is "Not Applicable" for any of the Items 13-14 or 16-18 then the subject will be deemed as "not applicable" for calculating scores.

Dermatology Life Quality Index

The DLQI is a 10-item validated questionnaire (Section 7.4) used to assess the impact of HS disease symptoms and treatment on quality of life (QoL). It consists of 10 questions evaluating impact of skin diseases on different aspects of a subject's QoL over the prior week, including symptoms and feelings, daily activities, leisure, work or school, personal relationships, and the side effects of treatment. Each item is scored on a 4-point scale (0 = not at all/not relevant; 1 = a little; 2 = a lot; and 3 = very much). Item scores are added to provide a total score, ranging from 0 to 30, with higher scores indicating greater impairment of QoL. For general inflammatory skin conditions, a change in DLQI score of at least 4 points is considered the minimum clinically important difference (MCID).

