4 INVESTIGATIONAL PLAN

4.1 Overall Study Design and Plan

This is a Phase 2, multicenter, randomized, double-blinded, parallel-group, placebo-controlled study to evaluate the efficacy and safety of upadacitinib in adult subjects with moderate to severe HS.

The duration of the study will be up to 57 weeks and will include an approximately 35-day screening period followed by a 48-week double-blinded treatment period and a 30-day follow up visit after the last dose of study drug.

Subjects who meet eligibility criteria will be randomized in a 2:1 ratio to 1 of the 2 arms as shown below:

- Upadacitinib 30 mg once daily (QD) (N = 40): Daily oral doses of upadacitinib 30 mg from the Baseline visit through Period 1 and Period 2.
- Placebo (N = 20): Placebo for upadacitinib from the Baseline visit up to the Week 12 visit (Period 1). At Week 12, subjects will be switched to blinded upadacitinib 15 mg QD through Period 2.

[figure not shown]

The schematic of the study is shown in Figure 1. Further details regarding study procedures are included in the Operations Manual (Appendix F).

See Section 5 for information regarding eligibility criteria.

The primary efficacy analysis will be conducted when all ongoing subjects have completed their Week 12 visit.

Figure 1. Study Schematic

HiSCR = ≥50% reduction from baseline in the total AN count, with no increase in abscess or draining fistula counts

PBO = placebo; UPA = upadacitinib

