5.8 Randomization/Drug Assignment

All subjects will be assigned a unique identification number by the IRT at the Screening Visit. For subjects who rescreen, the screening number assigned by the IRT at the initial Screening Visit should be used. The IRT will assign a randomization number that will encode the subject's treatment group assignment according to the randomization schedule generated by the statistics department at AbbVie.

Subjects will be randomized in a 2:1 ratio to 1 of 2 treatment groups:

- Upadacitinib 30 mg QD (N = 40)
- Placebo (N = 20)

Randomization will be stratified by anti-TNF use prior to baseline and Hurley stage (< III or III).

Subjects in the placebo group will be switched to upadacitinib 15 mg QD at Week 12.

All AbbVie personnel with direct oversight of the conduct and management of the trial (with the exception of AbbVie Drug Supply Management Team), the investigator, study site personnel, and the subject will remain blinded to each subject's treatment through Week 12. Sites and subjects will remain blinded for the duration of the study. In order to maintain the blind, the upadacitinib tablets and placebo tablets provided for the study will be identical in appearance. The IRT will provide access to unblinded subject treatment information in the case of medical emergency.

In the event of a medical situation that requires unblinding of the study drug assignment, the investigator is requested to contact the AbbVie TA MD prior to breaking the blind. However, if an urgent therapeutic intervention is necessary which warrants breaking the blind prior to contacting the AbbVie TA MD, the investigator can directly access the IRT system to break the blind without AbbVie notification or agreement. Unblinding is available in the IRT system via the Unblind Subject transaction, which is available only to the investigator. If the IRT system is unavailable, unblinding may occur by contacting the technical support of the IRT vendor via either phone (preferred) or email ([contact]). For country-specific phone numbers, please see the following website: http://www.endpointclinical.com/helpdesk/.

In the event that the blind is broken before notification to the AbbVie TA MD, we request that the AbbVie TA MD be notified within 24 hours of the blind being broken. The date and reason that the blind was broken must be conveyed to AbbVie and recorded on appropriate eCRF.

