APPENDIX D. ACTIVITY SCHEDULE

The following table shows the required activities across all visits. The individual activities are described in detail in the Operations Manual (Appendix F). Allowed modifications due to COVID-19 are detailed within the Operations Manual.

Study Activities Table

Activity	Day –35 to Screening	Day 1 Baseline	Day 15 Week 2 ^a	Day 29 Week 4 ^a	Day 57 Week 8 ^a	Day 85 Week 12 ^a	Day 112 Week 16 ^a	Day 168 Week 24 ^a	Day 224 Week 32 ^a	Day 280 Week 40 ^a	Week 48 ^a / Day 336 Premature Discontinuation	30-Day Follow Up Visit/Call
Visit Window	۵ ۵	Ď		Days	Ď	Ď	Ds	Ď	±7 Day		Ds	30 Vis
				Jays					± / Da\	13		
□ INTERVIEWS & (QUEST	IONNA	IRES									
Informed consent	✓											
Eligibility criteria	✓	✓										
Medical/surgical history	✓	\										
Hidradenitis suppurativa history	✓	>										
Alcohol and nicotine use	✓											
Adverse event assessment	*	*	*	*	*	*	*	*	*	1	*	*
Prior/concomitant therapy	1	1	1	1	1	*	1	*	1	*	*	1
Analgesic use (for HS-related pain) – daily from at least 7 consecutive days prior to Baseline and up to Week 16	*	*	*	*	*	*	*					
Patient Reported Outcomes (PROs): PGA Skin Pain— daily from at least 7 consecutive days prior to Baseline and up to Week 16; afterwards for 7 consecutive days leading up to each visit	*	1	*	*	*	*	*	*	1	*	*	

											ion	
Activity	Screening	Baseline	Week 2 ^a	Week 4 ^a	Week 8 ^a	Week 12 ^a	Week 16 ^a	Week 24 ^a	Week 32 ^a	Week 40ª	Week 48 ^a / Premature Discontinuation	w Up
	Day -35 to Day -1	Day 1	Day 15	Day 29	Day 57	Day 85	Day 112	Day 168	Day 224	Day 280	Day 336	30-Day Follow Up Visit/Call
PROs: HSSA – 7 consecutive days prior to Baseline, Week 2, Week 4, Week 8, Week 12, Week 16, Week 24, and Week 48/PD visits	~	V	V	*	*	*	V	*			*	
PROs: HSIA		✓		✓		✓	✓					
PROs: DLQI		✓				✓	✓					
Dispense handheld ePRO device and the paper diary (for Analgesic Use for HS-related pain)	*											
Collect handheld ePRO device											*	
TB risk assessment questionnaire	✓											
Review and document pregnancy avoidance recommendations with females of childbearing potential	*	*	1	*	*	*	V	*	*	*	*	
TLOCAL LABS &	EXAM	S										
Chest x-ray	✓											
12-lead ECG	✓											
Height (screening only) and weight	*	*	✓	*	*	*	*	*	*	*	✓	
Vital signs	✓	✓	✓	✓	✓	✓	✓	*	*	>	✓	
Physical examination	✓	✓				✓					✓	
Investigator assessments (abscess, inflammatory nodule, and draining fistula/tunnel count)		✓	✓	✓	1	1	√	✓	1	√		
Hurley Stage		✓				1			1			

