2.1 Individual Treatment Period Visit Activities

This section presents a list of activities performed during each visit, organized by visit. The dot pattern on the upper right indicates the place of the visit in the overall Treatment Period Activity Schedule.

Subjects will be allowed a visit window of \pm 3 days for all study visits (with the exception of the Baseline Visit, as the screening window is a maximum of 35 days) up to the Week 16 visit. Visits after the Week 16 visit will have a visit window of \pm 7 days.

Activities are grouped by category (Interview, Exam, etc.). Further information about each activity is provided in Section 3.

State of Emergency or Pandemic-Related Acceptable Protocol Modifications

During a state of emergency or pandemic situation, if it is not possible for all study procedures to be performed as specified due to travel restrictions or other reasons, the following modifications are allowed:

- If permitted by local regulations, the Institutional Review Board (IRB)/ Independent Ethics Committee (IEC), and the subject, some study visits and/or activities may be performed by phone/virtually. These are indicated by a hashtag (#) in the appropriate visit table(s) below.
- Some study visits and/or activities may be performed by a local clinic/hospital/laboratory. These are indicated by a plus sign (+) in the appropriate visit table(s) below. All procedures performed at local facilities must be performed by appropriately qualified personnel.
- Study visits and/or activities should be performed as scheduled whenever possible. If it is not possible to do so due to the pandemic, the following modifications should be followed:
 - The Screening, Baseline, and Week 12 visits should be performed on-site only.
 - If an activity is missed during a virtual visit, perform the activity at the earliest feasible
 opportunity. Laboratory draws for safety assessments should be obtained as soon as
 feasible and preferably within the protocol-defined visit window for the scheduled visit.
 Blood samples for PK assay that cannot be performed on-site for a specific visit will be
 considered missed.

No use or disclosure outside AbbVie is permitted without prior written authorization from AbbVie.

SCREENING:

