9.0 Efficacy Analyses

9.1 General Considerations

All efficacy analyses will be conducted in ITT Population in each period. All tests will be 1-sided at an alpha level of 0.05.

The Primary Analysis will be conducted after all ongoing subjects have completed Week 12, data pertaining to Period 1 has been cleaned, and a database lock has occurred for the purpose of efficacy and safety analysis in Period 1. This is the only and final efficacy analysis for Period 1.

In Period 1, all categorical variables at Week 12 and experience of flare in Period 1 will be analyzed using one sample Chi-square test comparing with historical placebo rate. Supplemental analyses will be conducted to compare in-trial data in upadacitinib group vs in-trial placebo data combined with historical placebo data for primary and secondary endpoints, and compare in-trial data in upadacitinib group vs in-trial placebo data for all categorical endpoints.

Continuous variables will be analyzed using Mixed-Effect Model Repeat Measurement (MMRM) (for endpoints other than DLQI) and Analysis of Covariance (ANCOVA) (for

DLQI) comparing with historical placebo mean change from Baseline at Week 12. Supplemental analyses will be conducted to compare in-trial data in upadacitinib group vs in-trial placebo data.

Long-term efficacy in the Period 2 will be summarized using the observed case approach.

Any subject who is randomized based on a wrong stratum will be analyzed according to the actual stratum the subject belongs to.

For variables other than PGA Skin Pain NRS, "Baseline" refers to the last non-missing observation on or before the date of the first administration of study drug or the date of randomization if no study drug is given. The "Baseline" of PGA Skin Pain NRS is defined as the last non-missing weekly average score, calculated based on the daily scores from the past 7 days (with non-missing values in 4 or more days of the 7 day period), before the date of the first administration of study drug or on or before the date of randomization if no study drug is given.

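### The written rule for the Week 12 skin-pain score does not stop at the Week 12 visit, so read literally it can average in days after placebo subjects have switched to upadacitinib 15 mg

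*Protocol*

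**What the plan says.** - **Weekly score.** Operations Manual 3.7 calculates the weekly PGA Skin Pain average "based on the 7 available daily scores from the days within each visit window that were closest to the nominal day". This is the only rule in either document for a post-baseline weekly pain score.
- **Baseline score.** SAP 9.1 defines Baseline separately, as the last non-missing weekly average "calculated based on the daily scores from the past 7 days (with non-missing values in 4 or more days of the 7 day period"), taken before the first dose.
- **Diary.** Protocol Appendix D schedules the pain item "daily from at least 7 consecutive days prior to Baseline and up to Week 16; afterwards for 7 consecutive days leading up to each visit". Operations Manual 3.7 adds that "PGA Skin Pain will be collected from subjects electronically every evening".
- **Switch.** For the placebo arm, Protocol 4.1 states: "At Week 12, subjects will be switched to blinded upadacitinib 15 mg QD through Period 2". Placebo runs from Baseline to the Week 12 visit. The upadacitinib 30 mg arm keeps its treatment.
- **Timing.** Week 12 is nominal Day 85 (Protocol Appendix D). Visits up to Week 16 may fall 3 days either side of the nominal day (Operations Manual 2.1).
- **Use of the score.** Under SAP 9.4.1, Week 12 NRS30 on upadacitinib 30 mg is tested mainly against a fixed historical rate of 22.5%. Supplemental analyses compare it with in-trial placebo alone and with in-trial placebo plus matched historical subjects. The in-trial placebo rate sets how many historical subjects enter: 68 up to 36%, 23 above 36% and up to 37%, none above 37%.
- **Cut at the switch.** SAP 10.2.1 ends Period 1 adverse-event attribution no later than the first Period 2 dose. No matching sentence exists for pain scores.

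**The concern.** Baseline is a look-back, while the general rule is centred on the nominal day. For most visits this is harmless. At Week 12 it matters, because the placebo arm changes treatment there and the diary continues without a break. A centred 7-day average would then combine days on placebo with days on upadacitinib 15 mg and label the result placebo at Week 12. The 30 mg arm has no such change, so the effect is one-sided.

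NRS30 is the only secondary endpoint, and the comparison with in-trial placebo is its only purely randomised analysis. The same placebo rate also drives the borrowing rule, where a small change can move the number of historical subjects from 68 to none.

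**Working it through.** **1. Which days the rule selects.** The nominal day is 85. The only numeric window printed is plus or minus 3 days, which gives Days 82 to 88, exactly 7 days. A wider symmetric window with a complete diary selects the same 7 days, since these are the closest to Day 85.

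**2. How many of them follow the switch.** For a visit on day v, the days strictly after it number 88 − v. Counting the visit-day evening score adds one.

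| Week 12 visit | Strictly after | Including visit-day evening |
|---|---|---|
| Day 82 | 6 | 7 |
| Day 83 | 5 | 6 |
| Day 84 | 4 | 5 |
| Day 85 | 3 | 4 |
| Day 86 | 2 | 3 |
| Day 87 | 1 | 2 |
| Day 88 | 0 | 1 |

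The item asks about the last 24 hours, so a visit-day evening score covers mostly pre-switch time. The middle column is the fairer count.

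**3. What a higher placebo rate would cost, on the SAP's own figures.** SAP Appendix F, section 3.2, assumes 46% on upadacitinib and a 26% historical placebo rate:

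| In-trial placebo rate | Power, in-trial only (45:23) | Power, 68 borrowed |
|---|---|---|
| 26% | 0.603 | 0.668 |
| 31% | 0.434 | 0.607 |
| Loss | 0.169 | 0.061 |

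As a check, exact enumeration of an unstratified two-proportion test at 45:23 gives 0.532 falling to 0.364 with unpooled variance, and 0.481 falling to 0.314 with pooled variance. The levels are lower than the SAP's, but the loss is nearly the same (0.168 and 0.167). The planned CMH test is stratified and was not rerun, so this does not show the SAP's figures to be wrong.

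**4. The borrowing rule.** Assume all 23 placebo subjects have baseline NRS of at least 3; the documents do not say so. Then 8/23 = 34.8% borrows 68 and 9/23 = 39.1% borrows none. The binomial probability of 9 or more responders is 0.118 at a true rate of 26% and 0.229 at 30%. One reclassified subject removes all borrowing only if there were exactly 8 responders before, which has probability C(23,8) × 0.26^8 × 0.74^15 = 0.11 at 26%.

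**5. How far the rate might move (illustration only).** None of these inputs is in the documents except the 26%:
- baseline pain normal with mean 6 and SD 1.8, held within 3 to 10;
- SD of change 1.5 to 2.5;
- every post-switch day lower by the same amount g.

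With 3 such days the weekly mean falls by 3g/7.

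| g (points) | Fall in weekly mean | Placebo NRS30 rate |
|---|---|---|
| 0 | 0 | 26% |
| 0.25 | 0.11 | 27% to 28% |
| 0.5 | 0.21 | 29% to 31% |
| 1.0 | 0.43 | 32% to 36% |

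**The case against.** The strongest reply is that the analysis window is not shown. The rule takes days within each visit window. The SAP speaks only of a pre-specified window and, in Appendix E (sections 2.1 and 2.4), ties it to the particular Study Period. Week 12 NRS30 is handled under Period 1 (SAP 9.2.1), placebo Period 1 ends at the Week 12 visit, and the lock covers Period 1 data. If the window respects the period, the closest available scores are those just before the switch, which is nearly the proposed definition.

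The same sentence also governs HSSA, which is collected only in the 7 days before a visit, and pain after Week 16, collected the same way. There it works as a look-back.

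This stands in part. It means a reader should not infer that the placebo rate will in fact contain on-drug days: a programmer may well cut at the switch. But no text applies the period boundary to this score, although the SAP does write such a cut for adverse events. Two programmers following the documents could derive different Week 12 responders and different borrowing counts.

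A second reply is that the main NRS30 test is untouched and that any bias cannot create a positive result. Both statements are correct, and they limit the point to supplemental analyses. A proof-of-concept study can still be misread in the negative direction.

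**Conclusion.** The concern holds as a gap in the definition. The one written rule for the weekly score permits post-switch days at Week 12: 3 of 7 for a visit on Day 85, and 0 to 6 over the permitted visit days. It also differs from the Baseline definition. The exposed results are the in-trial placebo comparison for NRS30, the combined-placebo comparison and the borrowing count.

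Two stronger readings are tempting and are not supported. The first is that the secondary endpoint's main result is compromised. It is not, because that test sets the 30 mg arm, which does not switch, against a fixed 22.5%. The second is that a bias of known size exists. The documents give no onset time for pain relief on 15 mg, so the movement in the placebo rate is unknown and is zero if there is no effect within a few days. The power figures above show what a 5-point rise would cost; they do not predict one.

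**What to change.** In SAP 9.4.1, define the Week 12 PGA Skin Pain score, in both arms, as the mean of the daily scores over the 7 days immediately before the Week 12 visit. Exclude any score recorded on or after the first Period 2 dose, and require at least 4 of 7 non-missing values, as at Baseline. Align Operations Manual 3.7 with this wording.

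The cost is one sentence in each document, settled before the Period 1 lock. No new data are needed, because the diary already covers these days.
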